#### **12.2.9.3. Analysis for Other Safety Objectives**

Each of the following events will be analyzed using the ITT population: pancreatitis, any cancer (excluding basal or squamous cell skin cancer), medullary thyroid carcinoma (MTC), C-cell hyperplasia, allergic/hypersensitivity reactions and discontinuation of study drug for any reason. The reasons for temporary discontinuation and reasons for permanent discontinuation of study drug will be summarized. Pancreatitis will be analyzed based on adjudicated events and on events as reported by investigators. The analyses of MTC and C-cell hyperplasia will be based on adjudicated events. The analysis of cancers (excluding basal or squamous cell skin cancer) will be based on events reported by investigators. The incidence will be summarized using frequency and percentage by treatment group and by visit. The frequency and percentage at each visit will be calculated as the number of patients and percentage of patients reporting the event at that visit. The overall frequency and percentage will be reported. The overall frequency and percentage will be calculated as the total number of patients and percentage of patients reporting the event during the entire study treatment period. Treatment group comparison will be assessed using a Chi-square or Fisher's exact test.

#### **12.2.9.4. Analysis of Laboratory Analytes**

Laboratory measurements collected at scheduled visits will be listed by patient by visit using all randomized patients. An additional listing will be presented for all laboratory measurements that are outside the SI units (International System of Units) normal range. Baseline for calcitonin, ALT, and hemoglobin A1c, will be Visit 1 and for serum creatinine, urine ACR and lipids will be Visit 3. All summary analyses will be based on the ITT population. Laboratory measurements that fall within a visit window will be associated with that visit. The laboratory measurement within the window that was taken closest to the visit date will be representative of that patient's lab value for that visit.

Unless otherwise specified, continuous laboratory measures will be analyzed using an ANOVA model on the rank-transformed data. The model includes treatment. Treatment group comparisons will be performed with no multiplicity adjustment. Categorical laboratory measures will be analyzed using Chi-square tests or Fisher's exact tests. For lipids (total cholesterol, LDL-C, HDL-C, triglycerides, and non-HDL-C) the summary analysis will be conducted based on the percentage change from baseline using an ANOVA model described above. The change from baseline will be used for the ratio of total cholesterol to HDL-C.

#### **12.2.9.5. Vital Signs**

Vital signs (SBP, DBP, and heart rate) will be collected 3 times in the seated position at each visit.

Measurements will be averaged for each patient at each visit; the average values will be used in the descriptive summaries and analyses.

Descriptive statistics for the actual measurements and change from baseline by treatment arm and visit will be presented. Summary analyses will be conducted using ITT population. The change from baseline will be analyzed using an MMRM model. The incidence of vital signs with selected thresholds will be summarized by frequency and percentage and compared using either a Chi-square test or a Fisher's exact test.

#### **12.2.9.6. ECG Analyses**

Both scheduled and unscheduled ECGs at each visit will be listed for all randomized patients. The ECGs will be qualitatively evaluated (see Section 10.2.3.3). The qualitative characteristics assessed will be summarized in the major categories of findings: normal ECG, abnormal ECG findings, and the subcategories of abnormal findings. The number of patients in each category will be compared between treatment groups and by visit using a Chi-square or Fisher's exact test.

#### **12.2.10. Analysis for the Additional Objectives**

For HbA1c, weight, and waist/hip ratio, an ANCOVA for the change from baseline to each visit and to endpoint (last available observation) will be performed for the ITT population. The model includes treatment as a fixed effect and the baseline value as a covariate. Missing endpoints will be imputed using a multiple imputation procedure on available postbaseline values of the variable. If there are no data after the date of randomization, the endpoint will be considered missing. The baseline data will not be used as an endpoint.

Time-to-event analyses will be performed for each of the following endpoints: the composite endpoint of death from CV causes, nonfatal MI, nonfatal stroke, or hospitalization for unstable angina; the composite endpoint of coronary, carotid, or peripheral revascularization and each of the components; and any hospitalization. A Cox proportional hazards regression model for the time to the first occurrence of the event, with treatment as a fixed effect will be performed for the ITT population.

Frequency counts and percentages of patients with fractures and patients, who developed cholelithiasis, will be presented for each treatment group and compared across treatment groups using Chi-square tests or Fisher's exact tests.

Cognitive function will be assessed in patients using the MoCA instrument and the DSST.

The DSST score is the number of correct number-symbol matches. The number attempted will also be recorded. Analyses of the last score and visit-specific analyses will be performed using ANCOVA for each continuous test measurement. The analysis will be based on change from baseline. Patients will be required to have a baseline and at least 1 postbaseline score to be included in these analyses.

The MoCA score is a continuous variable with a range of [0, 30]. It will be analyzed as a categorical variable using the categories: below the threshold for normal cognitive function (that is, mild cognitive dysfunction, MoCA score <26), and above the evaluation threshold (that is, normal cognitive function, MoCA score  $\geq$ 26).

Erectile function will be assessed in male patients. The International Index of Erectile Function (IIEF) scores will be used to assess for degree of erectile function. Changes from baseline to endpoint in total IIEF scores from the erectile function, orgasmic function, sexual desire, overall satisfaction, and intercourse satisfaction domains will be analyzed using an ANCOVA model that includes terms for treatment and the baseline values minus their mean as covariate.

### **12.2.11. Subgroup Analyses**

The effects of dulaglutide and placebo on the incidence of primary endpoint events will be examined across the following subgroups:

- Gender (Female vs. Male)
- Age (Age <65 years, and Age  $\geq$ 65 years)
- Prior CV event
- Duration of diabetes (Duration <5 years, 5 years  $\leq$  Duration <10 years, and Duration  $\geq$ 10 years)
- Body mass index (<median and  $\geq$ median)
- Baseline HbA1c (<median and  $\geq$ median)
- Geography (North America, South America, Europe, Asia, Other)

Forest plots of the hazard ratio will be provided for each subgroup. Other subgroups may be examined if determined to be of interest. As the number of these subgroups may be large, the probability of observing at least 1 statistically significant result just by chance is nontrivial. Thus, these analyses will be considered exploratory. All tests of interactions between treatment and subgroup will be conducted at a 2-sided alpha level of 0.10.

### **12.2.12. Interim Analyses**

The IDMC will be authorized to evaluate unblinded interim efficacy and safety analyses. Study sites will receive information about interim results ONLY if they need to know results for the safety of their patients.

Unblinding details are specified in the unblinding plan section of the SAP.

There will be 1 interim and 1 final analysis for this study. The interim analysis will occur when approximately 61% (730 events) of the expected number (1200) of primary endpoint events have accrued (Section 12.2.2).

Standard safety analyses of data from this trial will be conducted by the IDMC at regularly scheduled intervals. The IDMC will receive and consider information that is relevant to the safety of the participants in the study including results from other published studies. Anytime over the course of the trial, the IDMC may recommend stopping, pausing, or modifying the trial if it determines from its periodic safety reviews of data from this trial that dulaglutide harms patients or clearly benefits them.

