### **12.2.2. Trial Design**

There will be 1 interim analysis and 1 final analysis. The interim analysis will be performed when approximately 61% (730 events) of the positively adjudicated primary endpoint events have occurred. The final analysis will be performed at 100% (approximately 1200) of the positively adjudicated primary endpoint events, if the study is not stopped early. At the interim analysis timepoint ([Figure GBDJ.2](#)), superiority will be tested first; if successful, the trial may stop and superiority will be declared. Otherwise, the trial will continue to the end, where, at 1200 events, superiority will be tested followed by noninferiority. The interim and final analyses will be performed on unblinded study data. The interim analysis results and these decision rules are used by the IDMC as guidelines. If the interim analysis shows clear benefit of dulaglutide over placebo for the primary endpoint, the IDMC may recommend early termination of the study. Alternatively, if the boundaries are crossed at the interim analysis, the IDMC may still recommend the trial continue and not stop for early efficacy. At anytime during the trial, the IDMC could recommend stopping the trial for safety reasons. The alpha used across the analyses will be monitored by an O'Brien-Fleming spending function (O'Brien and Fleming 1979; Jennison and Turnbull 2000), (eg, with 730 events at the interim, 2-sided alpha = 0.0081). The alpha used at the final analysis will be adjusted to maintain the overall type I error control at a 2-sided significance level of 0.05. This will be accomplished using EAST software to calculate the alpha level for the final analysis considering the actual amount of information at the interim analysis (eg, with 1200 events at the final analysis, 2-sided alpha = 0.0475; overall power = 92.8%). If the true hazard ratio is as high as 0.85, this sample size would provide at least 80% overall power to show superiority. At the final analysis, superiority will be tested. The adjusted 95% CI for the hazard ratio will be calculated.

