There will be 1 interim analysis and 1 final analysis. The interim analysis will be performed when approximately 61% (730 events) of the positively adjudicated primary endpoint events have occurred. The final analysis will be performed at 100% (approximately 1200) of the positively adjudicated primary endpoint events, if the study is not stopped early. At the interim analysis time point (Figure GBDJ.4.1), superiority will be tested first; if successful, the trial may stop and superiority will be declared. Otherwise, the trial will continue to the end, where, at 1200 events, superiority will be tested followed by noninferiority. The interim and final analyses will be performed on unblinded study data by the Independent Data Monitoring Committee (IDMC) that will use the results and the foregoing decision rules as guidelines. Thus, if the interim analysis shows clear benefit of dulaglutide over placebo for the primary endpoint, the IDMC may recommend early termination of the study. Alternatively, if the boundaries are crossed at the interim analysis, the IDMC may still recommend the trial continue and not stop for early efficacy. At any time during the trial, the IDMC could recommend stopping the trial for safety reasons. The alpha used across the analyses will be monitored by an O'Brien-Fleming spending function (O'Brien and Fleming 1979; Jennison and Turnbull 2000), (for example, with 730 events at the interim, 2-sided alpha = 0.008; power 51.3%). The alpha used at the final analysis will be adjusted to maintain the overall type I error control at a 2-sided significance level of 0.05. This will be accomplished using EAST software to calculate the alpha level for the final analysis considering the actual amount of information at the interim analysis (for example, with 1200 events at the final analysis, 2-sided alpha = 0.048; overall power = 92.8%). At the final analysis, superiority will be tested followed by noninferiority. The adjusted 95% confidence interval (CI) for the hazard ratio will be calculated.

[figure not shown]

Figure GBDJ.4.1. Interim decision rule.

The median unbiased estimator for the hazard ratio will be reported if the trial is stopped early for efficacy at an interim analysis.

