4.3.6. Multiple Comparisons/Multiplicity Adjustments

The primary objective of this study is to demonstrate with statistical significance a clinically meaningful reduction in the incidence of primary endpoint events. There will be 1 interim analysis and 1 final analysis. The interim analysis will be performed when approximately 61% (730) of the primary endpoint events have occurred and have been adjudicated as such. The final analysis will be performed at 100% of the total information (approximately 1200 adjudicated primary endpoint events) if the study is not stopped early. Appropriate adjustments for multiplicity will be made to maintain an overall type I error rate of <0.05 (Section 4).

Multiplicity adjustments will be performed for the analyses on the primary and secondary efficacy endpoints in order to control the overall Type I error rate at a 2-sided alpha level of 0.05. For repeated testing of the primary outcome via interim analysis, an O'Brien-Fleming alpha spending function will be used to control alpha across the interim and final analyses for the testing of the primary endpoint (GBDJ Protocol Section 12.2.2). A graphical approach will be

used to control the type I error rate across the secondary endpoint analyses at the final analysis time point or at the interim analysis time-point if the decision is to stop the trial following the interim analysis (GBDJ Protocol Section 12.2.2 and Section 12.2.12 for the Interim Decision Rule).

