4.3.6.2.1. Data Cut-off Date for the Interim Analysis

The interim analysis is planned to be conducted when a minimum of 730 positively adjudicated MACE endpoints events have occurred. It is expected that there will be more than 730 events in the pool for the interim analysis, as all events that are adjudicated on the same day as the 730th positive event will also be included in the analysis. The data cut-off date for the interim analysis will be the event date, from the adjudicator's opinion, of the most recent event in this pool of unique subjects with positively adjudicated primary MACE endpoint events. In addition, all efforts will be made to adjudicate the majority of all MACE events with events dates prior to this cut-off date, and these adjudicated events will be included in the interim analysis (Figure GBDJ.4.4).

At the interim analysis, the alpha level used for the analysis will be determined based on the actual number of events included in the analysis using EAST Software (EAST 6, Cytel, www.cytel.com). If the trial continues to the end following an IDMC review of the interim

results, the final alpha will be adjusted based on the final number of primary MACE events using EAST software. If the IDMC recommends stopping the trial for efficacy following the interim analysis, analyses will be performed on this post-interim, final-lock database using the adjusted significance level alpha based on the Whitehead procedure (Section 4.3.6.2.2).

[figure not shown]

Figure GBDJ.4.4. Example of data cut-off date for the analysis of the primary MACE events.

4.3.6.2.2. Controlling Type I Error across Interim and Final Analyses Following Early Termination for Efficacy

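### Does the any-time clear-benefit wording in Protocol 12.2.12 open an unbudgeted efficacy look outside the 730-event interim?

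*Protocol*

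**What the plan says.** Protocol 12.2.12 counts one interim and one final analysis and refers to 12.2.2 for the interim. It then describes the IDMC's regularly scheduled safety analyses. The committee's power to recommend a stop, a pause or a modification has no limit in time there, and it applies "if it determines from its periodic safety reviews of data from this trial that dulaglutide harms patients or clearly benefits them".

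Protocol 12.2.2 places the efficacy decision at the interim: "If the interim analysis shows clear benefit of dulaglutide over placebo for the primary endpoint, the IDMC may recommend early termination of the study". For the rest of the trial it says "At anytime during the trial, the IDMC could recommend stopping the trial for safety reasons", and SAP section 4 repeats this: "At any time during the trial, the IDMC could recommend stopping the trial for safety reasons". Both sections describe their rules as guidelines for the IDMC.

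The alpha accounting is written for two analyses. SAP 4.3.6 chooses the O'Brien-Fleming form and states its scope: "alpha spending function will be used to control alpha across the interim and final analyses for the testing of the primary endpoint". SAP 4.3.6.2.1 opens the overrun procedure with "If the IDMC recommends stopping the trial for efficacy following the interim analysis". SAP section 4 adds: "The median unbiased estimator for the hazard ratio will be reported if the trial is stopped early for efficacy at an interim analysis".

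Regular IDMC review of efficacy is itself planned, in the Statistical Methods part of the Protocol synopsis and in Protocol 10.2.4. Protocol 8.3.5 leaves the decision to discontinue the study with the sponsor.

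**The concern.** Set side by side, the sections look inconsistent. One gives a benefit stop at any review with no threshold. The sections that define the alpha mention a benefit stop only at the interim. The committee will hold unblinded endpoint data by arm at each review, so the 12.2.12 route could be used.

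The two planned looks exhaust the two-sided 0.05. If a stop for benefit at some other review led to a superiority claim, the plan would state no level for the primary test at that review. It would state none for the secondary endpoints either, because the graph in SAP 4.3.6.1 takes its alpha from the primary test at the analysis in question. The Whitehead boundary and the median unbiased estimate would also have to be carried over to a situation that their text does not name. What would be at stake is the overall type I error of a claim that, under SAP 4.3.6.2.2, goes into labeling.

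**Working it through.** **Inputs.** Two-sided alpha 0.05, O'Brien-Fleming spending, 730 and 1200 events (Protocol 12.2.2); hazard ratio 0.82 (Protocol 12.1) and 0.85 (Protocol 12.2.2); 1:1 allocation (Protocol 9.3).

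**Step 1: reproduce the plan.** Information fraction t = 730/1200 = 0.6083, √t = 0.780. One-sided cumulative spending is 2[1 − Φ(2.2414/√t)], where 2.2414 is the normal quantile for 1 − 0.025/2.

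- Interim: 2[1 − Φ(2.874)] = 0.00406 one-sided, 0.0081 two-sided, z = 2.647.
- Final: solve P(Z₁ ≥ 2.647 or Z₂ ≥ c) = 0.025 with correlation 0.780. This gives c = 1.982, two-sided 0.0474 to 0.0475 (a last-digit rounding difference).
- Power at HR 0.82: mean of Z at d events is √(d/4)·|ln HR|. At the interim this is √182.5 × 0.1985 = 2.681, so power is Φ(2.681 − 2.647) = 51.3%. Overall power is 92.8%. At HR 0.85 overall power is 80.02%.

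All of this matches the stated 0.0081, 0.0475, 51.3%, 92.8% and at least 80%.

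**Step 2: what can lead to a claim.** Protocol 12.2.12 speaks of recommending. Superiority is declared only under Protocol 12.2.2 and 12.2.7 and SAP sections 4 and 4.13.2, at the interim or at the end of the trial. If those sections govern, the overall error is 0.05 whatever the committee discusses in between.

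**Step 3: suppose extra benefit looks did lead to claims and were not counted.** The documents give neither the number of looks nor a threshold, so these are assumptions. The planned looks stay at 0.0081 and 0.0475, and every crossing is taken as a stop and a claim. Overall error is twice the benefit-side crossing probability.

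| Extra looks (events) | Two-sided level at each | Overall error |
|---|---|---|
| 5 or 10 across the trial | 0.0001 | 0.0501 / 0.0502 |
| 5 or 10 across the trial | 0.001 | 0.0513 / 0.0521 |
| 3 or 6, all before 730 | cumulative spending at that event count | 0.0503 / 0.0509 |
| 1 at 900 | 0.001 | 0.0500 |
| 1 at 900, or 1 at 980 | 0.0081 | 0.0507 / 0.0504 |
| 1 at 600 | 0.01 | 0.053 |
| 10 evenly spaced | 0.01 | 0.076 |

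The 5 looks are at 150, 330, 520, 900 and 1080 events. The 10 in the first two rows are at 100, 200, 300, 430, 560, 650, 830, 930, 1030 and 1130. The looks before 730 are the first 3 and the first 6 of these. The last two rows are simulated.

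**Step 4: suppose the looks are counted.** The spending function then holds the overall error at 0.050. One look at 520 events gives levels 0.0013, 0.0077 and 0.0474, with power 80.0% at HR 0.85. Six looks before 730 give 0.0066 at the interim, 0.0473 at the end and power 79.98%.

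**The case for a change.** The best case for a change is that two sections of one protocol should not describe the same decision differently, and that one phrase would settle it. The IDMC charter might hold a threshold, but it was not supplied, and it would not align the protocol text. The documents also leave open whether a benefit decision at a periodic review is a look. Protocol 12.2.12 counts one interim, while the definition in Protocol section 4 is broad enough to take in any by-arm analysis before the final lock.

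The arithmetic can be made less comfortable. An uncounted look scored at the cumulative spending level gives 0.0542 at 900 events (two-sided 0.0193) and 0.0558 at 980 (0.0263). A counted look at 900 lowers the final level to 0.0438 and power at HR 0.85 to 79.6%, which misses the statement in Protocol 12.2.2: "If the true hazard ratio is as high as 0.85, this sample size would provide at least 80% overall power to show superiority".

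The difference in wording is real and stands. The larger figures carry little weight. Once 730 events have been analyzed, the spending rule gives 0.0169 at 900 and 0.0238 at 980, not the cumulative values. The one-sided 0.013 at 980 events in SAP 4.3.6.2.2 is an overrun boundary for a trial already stopped, and that section says it is not used if the trial continues. These scenarios also require a committee that adopts the spending function but declines to count the look. No document plans an efficacy look after 730, so there is no power figure to restate.

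**Conclusion.** No change is called for. The wording differs, but the sections do not contradict each other. Protocol 12.2.2 and SAP section 4 say what the IDMC may do and never say that a benefit recommendation is confined to the interim. Protocol 12.2.12 keeps the general remit that a monitoring committee with regular access to efficacy data would be expected to have. Formal testing stays under 12.2.2, and its figures (0.0081, 0.0475, 92.8%) reproduce.

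If a benefit stop between looks ever arose, analysts would have what they need. SAP 4.3.6.2.1 already sets the interim level from the actual number of events and adjusts the final level, and the same calculation gives a boundary at any event count. Counted in that way the error is 0.050, and before 730 events the cost in power is negligible.

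The size is close to nil if clear benefit is read strictly: 0.050 to 0.052 at p<0.001 or below. It reaches 0.076 only with ten uncounted looks at p<0.01, each leading to a claim that no section permits. Removing the phrase would cost the committee its stated freedom to act on clear benefit between looks. Writing in the alpha accounting would spell out what the spending function already allows and what the charter may contain. A cross-reference from 12.2.12 to the 12.2.2 boundary would be tidier, but no stated figure or conclusion depends on it.

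This rests on 12.2.2 and SAP section 4 governing any claim, and on the charter, which was not available, not saying otherwise.
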